## 1.0 INTRODUCTION

**1.1 Overview.** Survivors of cancers diagnosed during the adolescent and young adult (AYA) period (ages 15-39) are a largely understudied and underserved population. Although cancer-related mortality rates are declining among survivors diagnosed during childhood and later adulthood, the biologically and genetically distinct characteristics of cancers diagnosed during the AYA period places survivors of AYA cancers at increased risk for poorer treatment outcomes and chronic late effects. A cancer diagnosis during the AYA period, a life stage marked by formative changes, significantly disrupts a number of key life domains during a time of peak physical, psychological, and socioemotional development. These disruptions have the potential to exacerbate the post-treatment transition process, contributing to adjustment difficulties. As such, rates of distress are high in this age group and are compounded by feelings of isolation. Stress associated with negative psychosocial experiences can contribute to long-term maladaptive health behaviors, stress-related decrements in immune functioning, and overall lower quality of life. This represents an important unaddressed cause of cancer-related morbidity for this already vulnerable population. There are currently no evidence-based interventions in the years following treatment that tackle the key transitional issues commonly associated with the AYA developmental period. As such, this study proposes to test the effects of a highly scalable videoconferencing-delivered group program (Relaxation Response Resiliency Program; 3RP) aimed at mitigating the deleterious effects of stress by promoting stress management and coping among survivors of AYA cancers. Specifically, we propose to test the preliminary effect of an adapted 3RP (called 3RP-AYA) that dually supports stress management and addresses the unique needs of survivors diagnosed during the AYA period who are within 0-5 years from having completed cancer treatment.

**Importantly, the original 3RP is an established program developed at the Benson-Henry Institute for Mind Body Medicine (BHI) that has been tested with a variety of patient and provider populations (see 1.3); however, it has yet to be tested with survivors of cancers diagnosed during the AYA period.** To tailor and adapt the original 3RP, we conducted qualitative interviews with AYA survivors (protocol DF/HCC 17-315) to understand some of the 1) the psychosocial and transitional challenges AYAs face with early survivorship, 2) existing coping strategies, 3) their perceptions of the existing 3RP, 4) preferences for program content, structure, delivery modality (in-person, vs. phone vs. videoconference) and intervention schedule (e.g., program timing, session length, number), and 4) barriers to participation. Emerging findings from these interviews guided the adaptations to the program. Specifically, themes included the following: 1) the desire to have the program available as soon as AYAs complete cancer treatment; 2) an interest in learning a variety of mind-body tools with a preference for more active strategies (e.g., yoga); 3) inclusion of topics related to talking to others about their cancer experience; 4) inclusion of topics related to academic transitions; and 5) cognitive strategies to break patterns of rumination and manage uncertainty about the future. Based on some of these findings, we adapted the contents of the original 3RP to develop the 3RP-AYA. Moving forward in this protocol we will refer to this adapted program as the 3RP-AYA. As such, for this protocol, participants will be offered 8 weekly, virtually-delivered group 3RP-AYA sessions to test the feasibility, acceptability and preliminary effects of the 3RP-AYA (via self-report surveys). We will also examine the feasibility, acceptability and preliminary effects of collecting and analyzing objective physiologic data (hair cortisol; detailed in section 5.2.3a).

**1.2 Background and Rationale.** Survivors of cancers diagnosed during adolescence and young adulthood (AYAs) have poorer health outcomes. Approximately 70,000 AYAs (ages 15-39) are diagnosed with cancer yearly; cancer is the leading cause of disease related-deaths for AYAs. Due to the biological and genetic features of their cancer, and the timing of their diagnosis (i.e., a developmental period marked by physical and socioemotional changes), AYAs face poorer treatment outcomes and higher mortality rates. Survival rates for younger and older survivors have improved over the past 20 years, but mortality rates for AYAs remain unchanged.

AYAs are at increased risk for experiencing negative psychosocial and physical challenges associated with cancer treatment. The consequences of cancer and cancer treatment engenders challenges that are developmentally incompatible with the expectations associated with the AYA life stage. A cancer diagnosis during the AYA period significantly disrupts a number of key life domains during a time of peak physical and socioemotional development. Physical after-effects of treatment, such as chronic pain and fatigue, lead to functional impairments. As AYAs strive to rejoin their same aged-peers, they may have difficulty separating themselves from their cancer-identity, feeling isolated and “stuck” in their experiences.

Distress is prevalent in AYAs. The challenges of normative development coupled with the sequelae of cancer treatment can be overwhelming, triggering anxiety and depressed mood. Distress occurs when these stressors are not dealt with in an adaptive manner. As such, rates of distress are higher in this cohort compared to individuals diagnosed in early childhood and later adulthood. While acute symptoms persist for several years after treatment, peak levels of distress coincide with the first few years of completion.

Chronic, unmanaged stress can provoke widespread neuroendocrine and immune dysregulation. There is a well-established link between stress and health. Chronic stress stimulates activation of the sympathetic nervous system (SNS) and Hypothalamic-Pituitary-Adrenal (HPA) axis; chronic stimulation of these major stress systems can lead to decrements in immune functioning and poorer health states. However, the significance of these alterations has not been examined among AYAs, particularly those completing cancer treatment. Further, little is known how prolonged stress exposure during a sensitive period of development can impact physical and socioemotional well-being. In the unaffected population and adult survivors, stress is linked with increased risk for physical disease and poorer response to treatment.

Stress can also contribute to maladaptive health behaviors and quality of life impairments. Among AYAs, stress has been linked to physical inactivity, excess drinking, smoking, and substance use. Stress has also been shown to exacerbate the post-treatment symptoms AYAs experience, including pain, fatigue, and insomnia. These consequences increase AYAs risk for cancer-related morbidity and early mortality.

Despite their multiple vulnerabilities, there are a lack of targeted psychosocial programs that target their needs. Historically low research participation and their wide geographic distribution have made it difficult to identify AYAs and provide targeted treatment. The NCI and Livestrong Foundation have thus identified AYAs as a high priority population. The AYA-HOPE was the first to document high unmet needs among AYAs despite reported rates of distress, with 41% identifying psychosocial support as an unmet need.

[figure not shown]
Mind-body programs centered on the relaxation response (RR) may help mitigate the negative physiological effects of stress on AYAs. The RR is a physiological state characterized by decreased SNS arousal. Physiological changes associated with the RR are counter to the stress response. RCTs have found that RR elicitation may reduce adrenergic end-organ responsiveness, suggesting that it may enable people to remain relaxed under stressful conditions. RR practice has been shown to relieve stress-related conditions, such as migraines, chronic pain, and anxiety. The Relaxation Response Resiliency Program (3RP) is a mind-body program that was designed to promote stress adaptation and resiliency.

Mind-body strategies may also ameliorate the negative psychological and emotional effects of stress while assisting AYAs with managing the psychosocial challenges of early survivorship; however, efficacy remains unexplored. AYAs have shown interest in using complementary and alternative medicine (CAM), which encompasses mind-body approaches, to cope with stress and improve overall well-being; yet, there are no established interventions demonstrating the utility of these approaches for AYAs. Given their interests and the potential for mind-body approaches, research is needed to demonstrate the benefits of these approaches for AYAs. Currently, there are no known established interventions that aim to increase AYAs’ ability to cope and manage the specific psychosocial and developmental issues they face during the early post-treatment period.

This study thus attempts to address important gaps in the support of AYAs. It proposes to test the effects of a highly scalable, tailored, virtual program, the 3RP-AYA, for a group who is at highest risk for adverse physical and mental health outcomes yet who lacks access to targeted psychosocial resources. The program aims to reduce the harmful, whole-body effects of stress by integrating mind-body, positive psychology, and cognitive behavioral strategies to improve stress management among AYA survivors. These strategies have individually been shown to appeal to AYAs and improve the aftereffects of survivorship; however, no study has tested the combined effects of these approaches, as we propose to do.

**1.3 Intervention Schematic: The original 3RP framework (see Figure 1).** [name] (primary mentor) and colleagues at the Benson-Henry Institute for Mind Body Medicine (BHI) developed the *3RP Model* to explain how we can improve our ability to adapt to significant stress and life events, which we define as *resiliency*. The model asserts that resiliency is achieved by (1) promoting the relaxation response; (2) decreasing the stress response; and (3) promoting growth enhancement. Its corresponding program, the original 3RP, uses a blending of stress coping and cognitive behavioral treatment to achieve these goals. *Promoting the relaxation response* involves adopting strategies (e.g., guided imagery) to reduce heart rate, muscle tension, and breathing rate, in order to reduce our physiological response to stress. *Decreasing the stress response* entails increasing one's awareness of being in the stress response (negative thoughts, emotions, and behaviors) and learning skills to change/alter these components (e.g., cognitive restructuring and acceptance). *Promoting growth enhancement* involves learning adaptive strategies to increase self-acceptance, self-efficacy, healthy lifestyle behaviors, and social connectedness. This same model and key components underlie the 3RP-AYA.

**Figure 1 Relaxation Response Resiliency Model**

**Preliminary studies:** BHI investigators have demonstrated the efficacy of the 3RP in decreasing stress and improving psychological and physical health symptoms among patients with chronic pain, insomnia, infertility, and other medical symptoms. Recently, Drs. [name] and [name] adapted the 3RP and conducted an NCI-funded pilot with 28 cancer interpreters. Post-treatment follow-up results indicated improvements in job satisfaction ( $p=0.02$ ; Cohen's  $d=.41$ ) and stress reactivity (MOCS-A;  $p=0.13$ ; Cohen's  $d=.33$ ). [name] has also led a 3RP group treatment for a randomized trial (PI: [name]., Ph.D., DF/HCC 13-266) examining the efficacy of this treatment among patients diagnosed with the precursors of multiple myeloma. Currently, the feasibility of delivering a group 3RP virtually via Partners Health Care Telehealth videoconferencing software is being tested with parents of children with special needs (PI: [name], funded by the Dan Marino Foundation, Partners IRB Protocol #: 2016P001622). [name] is also currently conducting a study to assess the acceptability and feasibility of delivering the 3RP virtually for lymphoma survivors within 2 years of completing cancer treatment (DF/HCC 16-396 and DF/HCC 17-063).

[figure not shown]
## 2.0 OBJECTIVES

**2.1. Primary Aim:** To examine, in a pilot RCT (total  $n=72$ , goal of having approximately  $n=60$  completers), the feasibility and acceptability of an 8-session stress-management and resiliency group program (3RP-AYA)

delivered via videoconference technology for survivors of AYA cancer between the ages of 16-29 at study enrollment, but who were diagnosed between ages 14 and 29 and who are within 5 years of treatment completion. *Hypothesis 1:* The program will be **feasible** (defined by enrollment rate, session attendance and reported relaxation response elicitation practice) and **acceptable** (defined by program satisfaction, ease, and utility).

## 2.2. Exploratory Aims:

a) Using a randomized, waitlist controlled design, we will examine the preliminary effects of the 3RP-AYA on stress and stress management among AYAs. Specifically, we will examine the preliminary effects of the 3RP-AYA on psychosocial measures of mindfulness, depressed mood, anxiety and stress collected at three timepoints, as detailed below: T0 (baseline), T1 (IG: posttreatment, WG: baseline2), T2 (IG: 3 month follow-up, WG: posttreatment).

Exploratory *Hypothesis 2.2a:* Compared to the waitlist-controlled group (WG), the immediate start intervention group (IG) will demonstrate greater mindfulness, lower depressed mood, anxiety and perceived stress at post-treatment. Additionally, the immediate start intervention group (IG) and waitlist control group (WG) combined will demonstrate greater mindfulness, less depressed mood, anxiety and perceived stress at treatment completion (T0-T1 for IG; T1-T2 for WG).

b) We will explore the feasibility and acceptability of collecting hair samples to examine intervention-related changes in cortisol, a stress biomarker. *Exploratory Hypothesis 2.2b2b:* The 3RP-AYA group will demonstrate lower stress reactivity (as manifested by hair cortisol) at timepoint 1 (post-treatment for IG; baseline/waitlist period for WG).

c) In efforts to inform the literature and guide future studies on engaging AYA in psychosocial treatment, we, we will examine AYA reasons for deciding not to participate in this behavioral trial. *Exploratory Hypothesis 2.2c: Participants approached about the study who choose not to participate will do so for a variety of reasons, such as time constraints.*

## 3.0 RESEARCH SUBJECT SELECTION

Eligible participants include individuals who:

- 1) were diagnosed with cancer between ages 14 and 29;
- 2) completed cancer treatment within the past 5 years;
- 3) are between 16-29 years old at time of study enrollment.

*Exclusion criteria:* Patients will not be eligible if they are unable to speak or read English, are unwilling or unable to participate in the study, or are considered medically or otherwise unable to

participate by their oncology provider or study PI. Additionally, participants will be ineligible if they are unwilling or unable to participate in the 3RP-AYA session delivered online via Partners Health Care Telehealth Services videoconferencing software and if a patient has previously participated in sister-protocol DF/HCC #17-063.

Rationale for eligibility criteria: Although the accepted age range for AYAs (as defined by the IOM) is 15-39, our age range of 14- 29 for time of diagnosis was chosen in our efforts to target an adolescent and young adult population who was diagnosed during a time of great developmental change and important but stressful life transitions, including moving from childhood to older adolescence or young adulthood, graduating from high school or college, and entering financial independence (including no longer being eligible for parental insurance). Our range of 14-29 for age of diagnosis is also within the focal age-range identified by the NCTN-affiliated Children Oncology Group (COG) scientific committees that focus on AYA cancer. We believe this group may be particular susceptible to having difficulty accessing psychosocial care in the context of changes in insurance that happen around this time period). This was also a group, based on findings from our sister protocol (DF/HCC #17-063) that identified wanting a program such as the one described within. Our window for treatment completion (0-5 years) is consistent with the “early survivorship” period. These criteria will allow us to target a group who is most likely to experience increased psychosocial vulnerability and who demonstrates a high level of unmet needs. Patients who are within 5 years of completing cancer treatment and do not have evidence of residual disease, but who are receiving maintenance treatment (e.g. Rituxumab), may still be considered eligible for the study. Also, given our intentions to deliver this focus group via videoconference technology (i.e., Partners Telehealth), patients who are unwilling or unable to participate in the intervention delivered via Partners Telehealth software (due to lack of access to a mobile device, such as a laptop, computer, or mobile phone) will be ineligible. Importantly, we will closely document and monitor the numbers of individuals who are unable to participate given this criterion, as it will further inform the feasibility of this type of treatment modality. Lastly, though future work may examine the utility of this program among Spanish-speaking survivors and survivors of AYA cancers who speak other primary languages, we have chosen to include patients who speak English due to the breadth and exploratory nature of this pilot.

Inclusion Criteria	Exclusion Criteria
Diagnosed with any cancer between ages 14 and 29	Unwilling or unable to participate in the study
Completed cancer treatment within the past 5 years	Unable to speak or read English
Between 16-29 years of age at time of enrollment	Is medically or otherwise unable to participate (as determined by a physician or study PI)
	Unwilling or unable to participate in study sessions delivered via the Partners Telehealth videoconferencing software
	Participation in a focus group during Phase 1 (DF/HCC 17-315) or the sister-protocol (DF/HCC 17-063)

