## 5.0 STUDY DESIGN AND METHODS

### 5.1 Design / Study Type

This is a pilot RCT to examine the feasibility and acceptability of the 3RP-AYA among approximately 72 adolescent and young adult cancer survivors who are up to 5 years post-treatment. Participants who complete the baseline questionnaire and are randomized will be enrolled and counted toward the accrual goal of 72. As such, up to 72 participants may be enrolled in the study in order to allow approximately 60 patients to participate total in the intervention and waitlist arms (goal of 30 completer-participants per arm). Participants do not need to complete every study measure to be counted towards the 72-participant accrual goal (i.e., participants who only complete some measures/3RP-AYA sessions will still be counted towards the accrual goal); however, patients who do not complete any of the study measures or who do not participate in any intervention visits will not be counted towards this goal.

We plan to examine the proportion of patients who are eligible and the proportion who are found to be ineligible due to age, language, inability to use the videoconferencing software, oncologist refusal, and medically or psychiatrically unable to participate. Out of those who are eligible, we will examine the proportion of enrollments, refusals, lost-to-follow up, withdraws, and study completers. We will examine reasons for and rates of ineligibility and refusal, as these will inform the feasibility of the study and of delivering the program virtually. We will also examine the characteristics of non-completers and the circumstances of non-completion.

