### 5.2 Selection of Instruments (refer to section 5.5 for schedule of measures):

**5.2.1 Demographic Survey.** We will gather important demographic information to characterize our sample, including participants’ race, ethnicity, education, relationship status, health insurance, and annual household income (Appendix 8.17).

**5.2.2 Primary Outcomes.** 3RP-AYA Feasibility and Acceptability data will be collected electronically (via REDCap), on paper, or by phone:

**Feasibility:** Feasibility metrics are modeled after resiliency studies led with survivors and other medical populations. We will evaluate program feasibility by examining several process variables, including rates of study eligibility (percent of patients who are eligible), recruitment (number of eligible patients who express interest in our study), enrollment (percent of eligible pool who consents and enrolls), retention (percent of enrollees who complete the follow-up), and treatment adherence (number of days elicited relaxation response, number of participants who complete the follow-up surveys). We will also document reasons for ineligibility and refusal as well as sociodemographic characteristics, medical history, and cancer characteristics of refusers. Additionally, adherence to

recommended RR elicitation will be assessed via Weekly RR practice logs (Appendix 8.27). The Weekly RR practice logs are part of the standard 3RP program, and in order to reduce participant burden, only the questions about weekly RR elicitation, weekly appreciations, and stress, distress, and coping Likert scales are included, while the questions from the standard 3RP weekly practice logs about lifestyle behaviors (exercise and nutrition), social connectedness, and physical/emotional symptoms have been omitted.

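### The enrollment-rate denominator is contradictory: Section 3.0 makes unwilling people ineligible, while Section 5.1 counts refusals among the eligible

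*Combined protocol and SAP*

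**What the plan says.** Hypothesis 1 in Section 2.1 makes feasibility part of the primary aim, "defined by enrollment rate, session attendance and reported relaxation response elicitation practice". Section 5.2.2 sets the denominator of the first of these measures: "enrollment (percent of eligible pool who consents and enrolls".

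Who is eligible is set in Section 3.0. Its text says "Patients will not be eligible if they are unable to speak or read English, are unwilling or unable to participate in the study", and its table repeats the exclusion: "Unwilling or unable to participate in the study". A further exclusion in the same table reads "Unwilling or unable to participate in study sessions delivered via the Partners Telehealth videoconferencing software". The rationale in Section 3.0 repeats the videoconference exclusion, gives lack of access to a device as the reason, and promises to monitor the number of people unable to take part under it.

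Section 5.1 describes the participant flow differently: "Out of those who are eligible, we will examine the proportion of enrollments, refusals, lost-to-follow up, withdraws, and study completers". The people it plans to tabulate as ineligible are those "ineligible due to age, language, inability to use the videoconferencing software, oncologist refusal, and medically or psychiatrically unable to participate". Section 5.2.2 likewise names two categories: "We will also document reasons for ineligibility and refusal". The analysis plan in Section 6.8.1 refers to the proportions recruited, screened and enrolled, and gives no denominator.

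**The concern.** Someone who declines is unwilling. If Section 3.0 is applied as written, declining makes that person ineligible and removes them from the denominator of the rate that their refusal should lower. If Section 5.1 is followed, the same person stays in the denominator as an eligible refuser. Two screeners, each following a section of the same protocol, could report different enrollment rates from one log.

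The error can go only one way: moving refusers out of the eligible pool raises the rate. It matters most for people who could use videoconferencing but do not want it. The primary aim asks whether a program delivered in that format is feasible, so their refusal is evidence on the question itself. Section 3.0 makes them ineligible, Section 5.1 tabulates only inability to use the software, and no section assigns them to the refusals.

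**Working it through.** **Plan's own figure.** There is none to reproduce. The documents state no expected enrollment rate, no enrollment threshold and no expected number of refusals. The numerical feasibility threshold in Section 6.2 (75% of sessions) concerns attendance.

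**Sections side by side**

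| Person | Section 3.0 | Section 5.1 |
|---|---|---|
| Meets all other criteria, declines the study | Ineligible | Refusal among the eligible |
| Has a device, declines videoconferencing | Ineligible | Not named; only inability is listed |
| Cannot use the software | Ineligible | Ineligible |
| No response after three voicemails or emails (passive opt-out, Section 4.1b) | Not assigned | Not assigned |

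The first row is a direct contradiction. The second is a conflict with a gap, and the fourth is a gap.

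**Illustration of size**

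Inputs:
- E = 72 enrolled, the accrual goal in Section 5.1.
- R = number of refusers who meet all other criteria. This is an assumption: 216, 72 or 24.
- f = fraction of those refusers coded ineligible under Section 3.0. This is also an assumption.

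Formula: enrollment rate = E / (E + R(1 − f)).

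| R (assumed) | f = 0 (Section 5.1) | f = 0.25 | f = 0.5 | f = 1 (Section 3.0, literal) |
|---|---|---|---|---|
| 216 | 72/288 = 25% | 72/234 = 31% | 72/180 = 40% | 72/72 = 100% |
| 72 | 72/144 = 50% | 72/126 = 57% | 72/108 = 67% | 72/72 = 100% |
| 24 | 72/96 = 75% | 72/90 = 80% | 72/84 = 86% | 72/72 = 100% |

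The columns with f between 0 and 1 stand for mixed coding, for example where only videoconference decliners are coded ineligible. The last column is a ceiling. It supposes that every eligible person who did not enroll had stated unwillingness. Passive opt-outs have stated nothing, and people who consent but do not finish the baseline survey (required before enrollment, Section 4.2) have agreed to take part. Either group can remain in the pool without being enrolled, which keeps the rate below 100%.

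**The case against.** The strongest reply is that Section 5.1 is the most specific text on counting, and it keeps refusers among the eligible. Sections 5.2.2 and 6.8.1 also separate reasons for refusal from reasons for ineligibility, a distinction with little purpose if every refuser were ineligible. This stands as evidence of intent. A reader might infer from Section 3.0 that decliners definitely leave the denominator and that the rate is about 100% by construction; the documents do not support that. But the intent does not remove the conflict. Section 3.0 is where the criteria are listed, registration requires a completed eligibility checklist (Section 4.4), and Section 6.8.1 does not settle the denominator.

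A reader might also infer a contradiction with exploratory aim 2.2c, on reasons for not taking part. There is none. That aim is defined by who was approached, so it can be carried out however decliners are coded.

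On videoconferencing, the rationale ties the exclusion to lack of a device and promises to monitor the numbers. This answers the point for people without access. It does not cover those who have a device and decline the format, because the promised count is of people unable to take part.

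Finally, no stated decision turns on the enrollment rate, and since reasons are recorded, a reader might be able to recompute it. That limits the consequence. Recomputation works only if the log separates unwillingness from the other reasons for ineligibility, and the list in Section 5.1 has no line for it.

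**Conclusion.** The concern holds as an internal contradiction. Section 3.0 and Section 5.1 give incompatible denominators for a measure that defines primary feasibility, and literal use of Section 3.0 biases the rate upward. The case is clearest for people who could join by videoconference but decline it.

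The size of the bias cannot be determined from the documents. Under the assumed refusal counts, rates of 25%, 50% and 75% become 40%, 67% and 86% if half the refusers are coded ineligible, with 100% as the upper bound. No pass or fail result changes, because no enrollment threshold is set. What is at stake is the accuracy of a main output of a pilot that is meant to inform a later trial. The conclusion rests on the wording of the sections alone; only the illustration rests on assumed numbers.

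**What to change.** 1. In Section 3.0 (text, rationale and table), delete the words *unwilling or* from both exclusion criteria and keep *unable*.
2. In Sections 5.2.2 and 6.8.1, in line with Section 5.1, define the enrollment denominator as everyone who meets all the other inclusion and exclusion criteria, including the medical or provider criterion and the prior-participation criterion.
3. Count active refusers, and people who decline because of the videoconference format, as eligible and not enrolled, and show the reasons.
4. Report passive opt-outs who were never fully screened on a separate line, and show the rate with and without them. Sections 4.1b and 4.1d describe people at this outreach stage only as potentially eligible, so neither including nor excluding them is plainly correct.

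The cost is a wording change and matching codes in the screening log, with re-coding of any entries already logged as ineligible for unwillingness. Nothing protective is lost, since the consent process already prevents anyone from being enrolled unwillingly. The downside is that the reported enrollment rate may be lower.
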